## 11.3 Statistical criteria of termination of trial

A single statistical analysis is planned once all recruited subjects have completed the protocol (per-protocol). No interim analysis is planned for a test period of 14 days and no “stopping rules” are set from a statistical perspective. PI’s and clinician judgement are considered as reliable enough to stop the trial.

## 11.4 Planned Analyses

The analysis and documentation will be done by the statistician using R (version 3.3.2) a statistical software package. R “stats” package will be used for the confidence interval, non-inferiority, and Wilcoxon tests. Documentation of the analysis will be done with R Studio under R Markdown format.

### Main outcome: speech reception threshold

The paired t-test usually tests that the mean differences are zero. The non-inferiority test compares the difference to a non-zero quantity  $-\delta$ .

The assumptions of the paired t-test are:

1. The data are continuous (not discrete).
2. The data, i.e., the differences for the matched-pairs, follow a normal probability distribution.
3. The sample of pairs is a simple random sample from its population. Each individual in the population has an equal probability of being selected in the sample.

### Secondary outcome: APHAB questionnaire

Data from comparative questionnaire represent a ranking more than a magnitude. The data are not continuous and normality of the data distribution is not expected. Therefore, a non-parametric statistical method like the Wilcoxon signed rank test on repeated measures will be used.

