Objective(s):	The purpose of this research is to show that the performance of the device is as good as or better than the current device or previous hearing aid generation. Furthermore, speech should not be negatively affected with the addition of the new feature, the usability of the devices (that end users are able to handle the devices) should be as good as the current device, and there should be no artefacts or unwanted noises. Some measurements serve as quality control prior to product launch.

Outcome(s):	
Primary Endpoint:
 

Primary Outcome is the speech intelligibility with the investigational device compared to the current device (using speech tests)

 
Secondary Endpoints:
 

Comparing the subjective performance of the investigational device to the current device (using questionnaires)

Speech intelligibility with the new feature on and off (using speech tests)

Handling/usability of the devices (specified questionnaire)

Subjective preference testing (using interviews)

Procedural safety meaning that there are no unwanted noises or artefacts heard from the devices (as reported by the subjects)

 
Scores from speech tests and questionnaires should be as good as or higher than with previous devices. Handling of the devices should be the same or easier than previous devices. No unexpected, unwanted behaviour from the devices should occur.

Study design:	This is a controlled, open label, comparative clinical investigation conducted monocentric at the premises of Bernafon in Bern, Switzerland.

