## 9.2 Assessments of outcomes

### 9.2.1 Assessment of primary outcome

The primary outcome is the performance of the IMD compared with the RMD. It will be measured various times throughout the trial. The defining measurement will be on the 59th (+/-3d) of treatment when the subjects return to the clinic and will be measured with a questionnaire and lab tests. The results from this lab test will directly compare the IMD with the RMD as well as the unaided condition with no device. They will be compared to ensure that performance of the IMD is not poorer than the RMD.

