### 11.1 Hypothesis

The goal of the test is to show that the IMD performs at least as well as the marketed RMD. A superiority hypothesis is used when a difference between performances is expected. To show that two devices have the same effect, the Committee for Proprietary Medicinal Products (CPMP) (2005) recommends using a non-inferiority test.

The non-inferiority margin is computed from the findings of the testing performed on the current marketed RMD with the primary outcomes (SRT) and other published results summarized in a meta-analysis. Lower SRT indicates a better performance, i.e. a positive difference between unaided and aided indicates an improvement with amplification.

Test condition labels: the marketed RMD as the Control (C), the IMD as the Test (T), and the non-inferiority Margin ( $\delta$ ). Positive value of  $SRT_C - SRT_T$  indicates an improvement with T:

Under  $H_0$ : the IMD is not non-inferior to the RMD:

[figure not shown]
$$C - T \leq -\delta$$

Under  $H_1$ : the IMD is not inferior to the RMD:

$$C - T > -\delta$$

Non inferiority margin is set with the following rationale (S. Kaul et al., 2005): “One proposal for selecting the margin is to take one-half of the magnitude of the worst limit of this CI—the so-called “50% rule” or “95-95 method” recommended by the FDA” with unaided condition instead of placebo.

The reference effect (unaided-aided) is about 2 dB improvement ( $SD = 2$  dB). The lowest bound of the confidence interval is 1.3 dB. Following this rationale ( $\delta = E_{\text{95-95}} - 0.5 \times C_{\text{95-95}}$ ), we will set the non-inferiority margin to 1.3 dB. This rationale can be illustrated as follows (based on D’Agostino et al., 2003):

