## 11.2 Determination of Sample Size

For non-inferiority testing, sample size calculations are the same as those for a 1-tailed test for superiority when the specified  $\delta$  is the same as the superiority population difference to detect (Masha & Sessler, 2011). The sample size calculation follows the recommendation from Chow & Wang (2008), where  $sd$  is the standard deviation,  $\alpha$  the significance level,  $1-\beta$  the power, and  $\delta$  the non-inferiority margin:

$$n = \frac{sd^2 \times (z_{1-\alpha} + z_{1-\beta})^2}{\delta^2}$$

For 90% power at the 0.025 significance level, the required sample size is about 24 subjects to detect non-inferiority of the marketed RMD with an SD of 2 dB and non-inferiority  $\delta$  of 1.3 dB. (Chow & Wang, 2008, p. 52).

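### The planned Wilcoxon-type test on APHAB cannot show that the new device is no worse on questionnaires, and no margin or interval rule fills the gap

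*Protocol*

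**What the plan says.** **The aim.** The synopsis, under Outcome(s), states: "Scores from speech tests and questionnaires should be as good as or higher than with previous devices". Protocol 9.2.1 says that the defining day-59 assessment of the primary outcome "will be measured with a questionnaire and lab tests", and closes with "They will be compared to ensure that performance of the IMD is not poorer than the RMD". Under 9.3.5 and 9.3.6, APHAB is handed out at Visit 5 and collected at Visit 6, the day-59 visit.

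**The APHAB analysis.** Protocol 11.4, under the secondary outcome, says that "a non-parametric statistical method like the Wilcoxon signed rank test on repeated measures will be used". It states no null hypothesis, margin, alpha, sidedness, effect estimate or success rule. The SAP deals with SRT only and mentions no questionnaire.

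**The SRT analysis, for contrast.** Protocol 11.1 says that, for showing that two devices have the same effect, guidance "recommends using a non-inferiority test". Section 11.4 separates this from a test of zero difference: "The non-inferiority test compares the difference to a non-zero quantity", namely minus the margin. A margin and a one-sided hypothesis are given for SRT alone.

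**Software and status.** The opening of 11.4 says that the R stats package "will be used for the confidence interval, non-inferiority, and Wilcoxon tests". The synopsis (number of participants) and protocol 6.1 call the work exploratory.

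**The concern.** The questionnaire expectation is a statement of non-inferiority: equal or better is acceptable, worse is not. The named method answers a different question. A signed-rank test in its usual form can give evidence that scores differ, in either direction. It cannot give evidence that they do not differ, or that any worsening is small. Only a significant result favouring the IMD would bear on the aim, and protocol section 11 says that superiority is not expected, because the main functions are being ported from the RMD.

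With no margin and no interval rule, a non-significant p-value is the only result of the planned test that could be taken to stand for equality. That reading rewards thin data: the fewer or noisier the APHAB pairs, the easier it is to reach. Several provisions reduce the number of pairs. Section 11.5 restricts the analysis to complete cases and removes data when the principal investigator doubts that APHAB was understood. Section 8.4 discards data after insufficient wear. At stake is a questionnaire claim that the data might not support, in a study whose results the sponsor intends to use as proof of performance (1.1).

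**Working it through.** **Step 1. The plan's own sample size.** The only sample size in the documents is for SRT: "For 90% power at the 0.025 significance level, the required sample size is about 24 subjects". The formula in 11.2 is n = [sd × (z₁₋α + z₁₋β) / δ]², with sd = 2 dB, z₀.₉₇₅ = 1.960 and z₀.₉₀ = 1.282.

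- δ = 2 − 1.31/2 = 1.345 (SAP 3.1, unrounded): n = 23.2, rounded up to 24.
- δ = 1.34 (SAP 4): n = 23.4, rounded up to 24.
- δ = 1.3 (protocol 11.2): n = 24.9, rounded up to 25.

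The figure of about 24 is reproduced. It says nothing about APHAB, for which neither document gives an SD, a margin, an alpha or a required number.

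**Step 2. What a non-significant APHAB result would mean.** Assumptions, none of them supplied by the plan: paired IMD−RMD differences are normal, the test is an exact two-sided signed-rank test at 5%, and the true worsening is expressed in SDs of the paired difference. I use n = 24 (the SRT requirement), n = 35 (approximate enrolment in the synopsis), and n = 20 to show the effect of losing pairs. There were 20,000 simulated trials per cell, so the Monte Carlo standard error is at most √(0.25/20,000) = 0.35 percentage points.

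Chance that the test is not significant:

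| True worsening | n=20 | n=24 | n=35 |
|---|---|---|---|
| none | 95% | 95% | 95% |
| 0.2 SD | 87% | 85% | 81% |
| 0.3 SD | 77% | 72% | 61% |
| 0.4 SD | 62% | 55% | 39% |
| 0.5 SD | 46% | 37% | 19% |
| 0.65 SD | 24% | 15% | 5% |

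The last row is the ratio of the SRT margin to its SD, 1.3/2 = 0.65. It is only a yardstick, because nothing in the documents carries that ratio over to APHAB. In every row with a true worsening, a smaller sample makes non-significance more likely.

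**Step 3. What a margin-based reading would do.** The same signed-rank procedure is shifted to test against minus a margin, one-sided 0.025. This corresponds to asking whether the 95% Hodges-Lehmann interval clears the margin. The margins are assumed. When the true worsening equals the margin, the simulated error is 2.2% to 2.5%. When there is no true difference, the chance of success is:

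| Assumed margin | n=24 | n=35 |
|---|---|---|
| 0.3 SD | 28% | 38% |
| 0.4 SD | 45% | 62% |
| 0.5 SD | 63% | 80% |
| 0.65 SD | 85% | 96% |

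At 0.5 SD and n=24, for example, treating non-significance as success would accept a device that is truly 0.5 SD worse 37% of the time. The margin-based test would do so about 2.5% of the time.

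**The case against.** **No rule equates non-significance with success.** A reader might infer that the plan will declare questionnaire non-inferiority from p>0.05. The documents do not say that. The null of no difference is itself implied by the usual form of the test rather than written out, and the method is named only as an example of its kind. What stands is that the result could be so read and that nothing prevents it.

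**An interval is mentioned.** A reader might infer that no confidence interval is planned at all. That goes too far: the opening of 11.4, which covers both outcomes, lists one among the uses of the software. It is not tied to APHAB, and the 95% interval in 11.4.3 concerns switching to superiority.

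**The questionnaire's role is limited.** A reader might take 9.2.1 to make APHAB part of the primary endpoint. That section says only that a questionnaire is used, and its closing sentence follows directly on the lab-test results. Sections 5.1 and 11.4.2 define the primary outcome as SRT. The synopsis sentence is a general expectation, not a formal hypothesis, and the analysis is called exploratory. This lowers the weight. It does not remove the mismatch between an expectation of equal or better scores and a test that cannot support it.

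**The percentages depend on assumptions.** Section 11.4 does not expect APHAB data to be normal or continuous, and the simulation assumes normal differences. It would be too strong to say that a real worsening is likely to be missed: that holds for small shifts, and at 0.65 SD the chance is 15% or 5%. The documents do not establish which shift matters.

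**The data are described as closer to a ranking than a magnitude.** That might seem to argue against an estimated difference. However, the signed-rank test already ranks the sizes of the paired differences, and the Hodges-Lehmann interval inverts that same test.

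**Conclusion.** The point holds at modest severity. The protocol expects questionnaire scores to be no worse, names for APHAB only a test whose standard null is no difference, and supplies no margin, success rule or APHAB interval. The protocol's own reasoning in 11.1 calls for a different approach when sameness is to be shown. The SAP does not fill the gap.

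The mismatch itself follows from the text and needs no assumption. Its size can only be illustrated: under the assumptions in step 2, the chance of non-significance despite a true worsening runs from 72% / 61% (n=24 / n=35) at 0.3 SD, through 55% / 39% at 0.4 SD and 37% / 19% at 0.5 SD, to 15% / 5% at 0.65 SD. The SRT non-inferiority test is not affected, nor does the plan commit the sponsor to misreading a non-significant result.

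**What to change.** Before the data are analysed, amend the APHAB paragraph of protocol 11.4 and carry the text into the SAP:

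1. Make the Hodges-Lehmann paired difference (IMD−RMD) with its 95% confidence interval the main APHAB result, taken from the same Wilcoxon procedure.
2. Name the APHAB score analysed and the direction that is favourable. State that each subject rates both devices, and when: 9.3.5 hands the form out at Visit 5 without saying for which device.
3. State that p>0.05 does not support a conclusion that the IMD is as good as the RMD.
4. Choose one of two routes. Either pre-specify and justify an APHAB margin against which the interval is read, or label APHAB descriptive and draw no conclusion of sameness from it. Without one of these, the reading of the interval is left to judgement after the fact.

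The cost is small. The interval is an option of the Wilcoxon function in the R package already named. The text is a short paragraph in 11.4 and a short new section in the SAP, which has no questionnaire section to edit. The downside is that the claim may weaken if the interval is wide. Under the step 3 assumptions, with no true difference and n=35, it would clear a 0.3 SD margin 38% of the time and a 0.5 SD margin 80% of the time. If no defensible margin can be given, the descriptive route is the safer one.

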#### 11.4.1 Datasets to be analyzed, analysis populations

Analysis population: a single group that had the same treatment (per protocol set).

The included subjects are experienced hearing aid users (minimum 6 months) with the same hearing aid model across the population. As hearing loss does not normally fluctuate, we assume that their hearing capabilities are stable over time and that the performance with a hearing aid can be compared over a longer period without any wash out period. Subjects' individual auditory capacities (hearing loss degree, noise tolerance, speech recognition) vary, however the sample is considered as a homogenous population regarding their experience with the RMD. It will be ensured that the acceptance to generic amplification via hearing aids is not tested but an actual evaluation of the difference between the RMD and the IMD. A single assignment treatment will be considered representative of clinical intervention, i.e. when an experienced hearing aid user acquires a new device.

[figure not shown]
#### 11.4.2 Primary Analysis

Speech Reception Threshold (SRT) will be measured in a single lab test under three test conditions: unaided, control (RMD), and test (IMD) after appropriate training. Test condition order will be randomized using a Latin square design to control any potential order effect. The difference between control and test condition will be compared to the non-inferiority margin to test for non-inferiority. The unaided condition will be used as control of the investigational device benefit if non-inferiority could not be shown.

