### 7.3 Assignment to study groups

For the field tests the allocation to the groups will be randomized using stratification in order to maintain balance between the two test groups. The stratification will be based upon the hearing loss of the participants, and more specifically the pure tone average and individual frequency lowering prescription (on/off). The idea is to avoid that any results are affected by one of these factors being more heavily represented in one group versus the other. For lab tests the assignment to the test condition will also be randomized. The test condition order will be randomized using a latin square design. This will minimize the bias created when one test condition is tested in the first or last position all of the time.

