### 9.3.6 Sixth Visit

Visit 6, Testing/Final, Day 59 +/- 3: The subjects will hand in the questionnaires given to them at the previous appointment. The clinician will conduct an interview based on the comments in the diary and prepared questions about user experience. A lab test will be made to test speech intelligibility with the OLSA. They will test in three conditions: unaided, aided with the RMD, and aided with the IMD. Any AEs will be reported in the CRFs. They will be told that the trial is complete.

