3.2 Non-inferiority test hypothesis

Lower SRT indicates a better performance, i.e. a positive difference like between unaided and aided shows an improvement with amplification. Following values definition: The current marketed device is the control: C,

The investigational device is the test: T,

The non-inferiority margin: M.

So if C-T < 0 then C is better than T and if C-T > 0 then T is better than C.

Test Hypothesis

Under H0: C - T <= - M, i.e. non-inferiority not found

Under H1: C - T > - M, i.e. T significantly non-inferior to C

Test analysis

[figure not shown]
The paired t-test usually tests that the mean differences are zero. The non-inferiority test compares the difference to a non-zero quantity -M.

The assumptions of the paired t-test are:

- 1. The data are continuous (not discrete).
- 2. The data, i.e., the differences for the matched-pairs, follow a normal probability distribution.
- 3. The sample of pairs is a simple random sample from its population. Each individual in the population has an equal probability of being selected in the sample.

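### The plan does not fix the orders of unaided, RMD and IMD testing; using all six orders equally, rather than a single Latin square, would keep unaided carryover out of the primary contrast at no cost in subjects or tests

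*Protocol*

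**What the plan says.** At Visit 6 (Protocol 9.3.6) each subject takes the OLSA three times: "They will test in three conditions: unaided, aided with the RMD, and aided with the IMD". Protocol 11.4.2 places these in one session; the speech reception threshold (SRT) "will be measured in a single lab test under three test conditions: unaided, control (RMD), and test (IMD) after appropriate training".

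On order, 11.4.2 says "Test condition order will be randomized using a Latin square design to control any potential order effect" and 7.3 says "The test condition order will be randomized using a latin square design". Section 7.3 adds the reason: "This will minimize the bias created when one test condition is tested in the first or last position all of the time". That is an aim about test position. Neither section lists the orders, says how many squares are used, or mentions the preceding condition. The SAP does not discuss test order.

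The primary comparison in 11.4.2 is unadjusted: "The difference between control and test condition will be compared to the non-inferiority margin to test for non-inferiority". SAP 3.2 makes it a shifted paired t-test: "The non-inferiority test compares the difference to a non-zero quantity -M". No term for order or carryover is named in either document.

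**The concern.** A 3x3 Latin square puts each condition once in each position, but it does not balance what each condition follows. Within one such square, a condition that is not first always follows the same other condition. The unaided run therefore comes directly before one device repeatedly and before the other never.

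The unaided run is not part of the RMD-IMD contrast. Under 11.4.2 it is used only if non-inferiority is not shown. If it leaves any effect on the next SRT that differs from the effect an aided run leaves, that effect enters the mean device difference as bias. The bias does not shrink with more subjects. Its direction depends on which square was drawn and on the sign of the carryover, so it could raise the chance of a false non-inferiority claim or cost power.

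**Working it through.** **The plan's own figure.** SAP section 4 uses n = [SD(z0.975 + z0.90)/margin]², with SD 2 dB, one-sided alpha 0.025 and power 90%. The margin from SAP 3.1 is 2 − 1.31/2 = 1.345, which SAP section 4 prints as 1.34. Then (2 × 3.2415/1.345)² = 23.23, rounded up to 24, which reproduces the plan. With the rounded margin of 1.3 dB the formula gives 24.87, rounded up to 25. The calculations below use SD 2, margin 1.3, one-sided alpha 0.025, n = 24, and n = 35 (the approximate enrolment in the synopsis).

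**Orders.** Write U for unaided, C for RMD and T for IMD. The two possible squares are:

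- Square A: UCT, CTU, TUC. C follows only U, and T follows only C.
- Square B, the mirror: UTC, TCU, CUT. T follows only U, and C follows only T.

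**Expected value of C − T.** Model each SRT as subject + position + condition + λ of the preceding condition, where λ is the effect in dB on the next SRT. Averaging C − T over the orders:

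- Square A: position terms cancel; bias = (2/3)(λU − λC).
- Square B: position terms cancel; bias = (2/3)(λT − λU).
- All six orders equally: position terms cancel; bias = (1/3)(λT − λC). The coefficient of λU is zero.

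**Illustration.** The documents give no λ. Assume an unaided-specific carryover of 0.1, 0.25 or 0.5 dB, with λC = λT = 0. Bias is two thirds of the assumed value. Error and power come from the noncentral t with n − 1 degrees of freedom. The noncentrality is bias × √n/2 when the true difference lies at the margin, and (1.3 ± bias) × √n/2 when the devices are equal. For example, 0.333 × √24/2 = 0.816 gives a type I error of 0.120.

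| Assumed carryover (dB) | Bias, one square (dB) | Type I error if it favours IMD, n = 24 / n = 35 | Power if it goes against IMD, n = 24 / n = 35 |
|---|---|---|---|
| 0 | 0 | 0.025 / 0.025 | 0.862 / 0.962 |
| 0.1 | 0.07 | 0.036 / 0.039 | 0.825 / 0.943 |
| 0.25 | 0.17 | 0.058 / 0.069 | 0.758 / 0.903 |
| 0.5 | 0.33 | 0.120 / 0.158 | 0.621 / 0.793 |

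Under the same assumption, all six orders in equal numbers give zero bias.

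**Precision.** In a least-squares fit with subject and position effects, where σ² is the within-subject variance of one SRT, the variance of C − T is 2σ²/N for one square and for six orders alike. With carryover terms added it is 10σ²/N for one square and 2.5σ²/N for six orders.

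**Uneven numbers.** With N completers, the coefficient of λU is (number with U directly before C − number with U directly before T)/N. At 24 it is 0, with four subjects per order. At 35, spread as evenly as possible, it is at most 1/35 = 0.029, against 0.667 for one square.

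**The case against.** The strongest reply is that the text never says one square. With 24 to 35 subjects any square has to be repeated, and mirror squares or a fresh random square per block of three would also fit the wording. The remedy is itself a pair of Latin squares. This stands: a reader might infer that the plan uses only three orders, and the documents do not show that. Leaving it open still has a price. With a fresh random square per block at n = 24 (eight blocks), all blocks share one square with probability only 2 × 0.5⁸ = 0.008. An exact 4/4 split has probability only 0.27, and the mean absolute λU coefficient is (2/3) × 0.273 = 0.18.

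A reader might also infer that carryover could never be separated from the device effect with three orders. That is wrong. A model with subject, position, device and first-order carryover is estimable from one square, at 10/2 = five times the variance. The bias belongs to the planned unadjusted test; no carryover model is planned.

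Nor is it fair to call the order statement in 11.4.2 false without qualification. Section 7.3 explains the aim as position balance, and a Latin square delivers that.

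The mechanism may be weak. The SAP describes an adaptive test at the 50% threshold, which tends to equalise difficulty between conditions, and 11.4.2 provides for training. Fatigue that builds equally after every run makes the three λ equal, and the bias is then zero in either square. Only a carryover specific to the unaided run matters here, and no passage documents one. Equally, nothing excludes one. The remark in 11.4.1 that performance "can be compared over a longer period without any wash out period" concerns long-term device use, not successive runs in one session.

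Finally, power at n = 24 understates the plan if about 35 subjects complete. That is correct for power (0.962 before any bias), but type I inflation is larger at 35 than at 24.

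**Conclusion.** The point holds as a free improvement, not as a demonstrated error. A list built from a single 3x3 square would satisfy 7.3 and 11.4.2 and would leave the unaided carryover unbalanced between the devices, with a bias in C − T of two thirds of a carryover difference. That algebra is exact under additive first-order carryover and the unadjusted paired test.

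The effects on error and power are illustrations. They rest on an assumed 0.1 to 0.5 dB carryover specific to the unaided run, SD 2 dB, margin 1.3 dB and the least favourable list. They should not be read as an estimate of what will happen in this trial.

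It would also be too much to say that six orders remove all carryover. A residual of (1/3)(λT − λC) remains, which is close to zero only if the two devices carry over alike. When λU = 0 and λT = −λC, the six orders leave the same absolute bias as one square.

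**What to change.** In Protocol 7.3 and 11.4.2, replace the reference to a Latin square with a statement that all six orders of unaided, RMD and IMD (two mirror Latin squares) will be used equally, allocated at random in blocks of six.

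The cost is one sentence in each section and a different randomisation list. The number of subjects, the three tests per subject and the variance of C − T stay the same. Exact cancellation needs equal numbers of completers in each order, hence a multiple of six such as 24, 30 or 36. With 35 evenly spread, a 0.5 dB unaided carryover would leave at most 0.029 × 0.5 = 0.014 dB.
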